### 8.5.5 Beam selection and geometry, planning technique and treatment delivery

In general, beams should be chosen to preserve OAR constraints and provide adequate PTV dosing (D95  $\geq$ 95% of the prescription dose), while respecting mechanical constraints of equipment. No minimum number of beams is necessary. Coplanar and non-coplanar beams are permitted.

Any form of external beam radiotherapy is acceptable (high energy photons, electrons, or protons), provided the dose is expressed in cobalt-Gy equivalent (CGyE) or Gy equivalent. Beam energy should be chosen in consideration of penetration depth, neutron contamination, etc. To account for the radiobiologic effectiveness of electrons, investigators are encouraged to prescribe the radiation dose to the 90% isodose line that encompasses the PTV.

Radiotherapy must be planned in 3-dimensions, and dose-volume analyses are required to ensure OAR constraints and PTV coverage is adequate. For 3D conformal planning, both physical and dynamic wedges can be used. Both MLC and block could be used for beam confinement when using photons.

Planning and treatment delivery can be carried out using any technique (non-conformal, conformal, intensity-modulated, volume modulated arc, etc) using any mechanism of external beam radiation delivery (linear accelerator, CyberKnife™, etc).

Use of tissue equivalent bolus to ensure adequate build-up is permitted for the treatment of superficial targets.

Verification of accurate subject positioning for treatment must occur through the generation and assessment of imaging (MV port films, kV images, cone beam CT, etc) or direct inspection of light fields (for electron beam therapy). Conventional subject setup with skin tattoos or optical surface imaging can only be used as initial subject alignment, but not final positioning.

### 8.5.6 Radiotherapy timing and dose fractionation

Treatment will be initiated after the first dose of immunotherapy, but before the second dose of immunotherapy.

Subjects receiving 27 Gy in 3 fractions should be scheduled to receive treatment on non-consecutive weekdays, no more than 2 days/week, over no more than 14 days. Ideally, treatment will be given with 2 days between treatment (Monday/Thursday/Monday, Tuesday/Friday/Tuesday, Monday/Friday/Tuesday, or Tuesday/Friday/Wednesday schedule).

Subjects receiving 30 Gy in 10 fractions should be scheduled to receive treatment on consecutive weekdays, no more than 5 days/week, over no more than 14 days.

Dose modifications for radiotherapy as a result of toxicity-are-allowed per the Investigator's assessment.

CONFIDENTIAL

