### 3.1.6 Sample Size and Statistical Considerations

This study is intended to generate descriptive safety data. Nine subjects are anticipated for each cohort to enable a variety of disease presentations and RT targets.

Prior experience with nivolumab and ipilimumab administered in combination has been associated with a treatment-related grade 3/4 toxicity rate of 53%. A rating of Grade 3/4 drug- or radiation-related toxicity is considered to be acceptable in Cohort A if  $\leq 7$  of 9 subjects (78%) are affected (see exception in Section 3.1, i.e., asymptomatic amylase and lipase abnormalities are not included). This number was selected to avoid premature closure of exploration of this approach.

As this is the first prospective study of RT plus ipilimumab and nivolumab, no historical controls are available to anticipate the rate of toxicity of this triple combination regimen.

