**Table 1. Treatment Schema**

Cohort N	Week	Checkpoint Antibodies (IV)		Radiotherapy
		Ipilimumab a	Nivolumab b	
Cohort A n = 9	1	3 mg/kg	1 mg/kg	30 Gy delivered over 2 weeks in 10 fractions of 3 Gy each
	2	–	–	
	4, 7, 10	3 mg/kg	1 mg/kg	–
	12, 14, 16, 18	–	240 mg	–
	20+ b	--	240 mg Q2W or 480 mg Q4W	--
Cohort B n = 9	1	3 mg/kg	1 mg/kg	27 Gy delivered over 2 weeks in 3 fractions of 9 Gy each
	2	–	–	
	4, 7, 10	3 mg/kg	1 mg/kg	–
	12, 14, 16, 18	–	240 mg	–
	20+ b	--	240 mg Q2W or 480 mg Q4W	--

RT will be initiated after the first dose and before the second dose of immunotherapy.

Abbreviations: Gy = Gray; kg = kilogram(s); mg = milligram(s); N = number; IV = intravenously; Q2W = every 2 weeks; Q4W = every 4 weeks

a Administered once every 3 weeks for 4 doses. (3-week cycles)

b Administered once every 3 weeks for 4 doses (at 1 mg/kg) and then 240 mg once every 2 weeks.

Note: per Amendment 5, nivolumab monotherapy continuing after Week 18 may be given as 480 mg every 4 weeks, starting on Week 20, followed by Weeks 24, 28, etc.

See Section 6.1 for order of infusion.

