### 3.1.8 Dosing Adjustments, Delays, and Discontinuations

Dosing adjustment, delays, and discontinuations of RT should be managed in accordance with standard of care. See Section 6.2 for administration details.

Dosing reductions in response to toxicities of ipilimumab or nivolumab are not permitted. Dosing delays and discontinuations of ipilimumab and nivolumab should be managed in accordance with Section 8.3. The following documents may also be referenced:

- YERVOY® (Ipilimumab) Package Insert: [http://packageinserts.bms.com/pi/pi\\_yervoy.pdf](http://packageinserts.bms.com/pi/pi_yervoy.pdf)
- YERVOY® (Ipilimumab) Immune-mediated Adverse Reaction Management Guide: <https://www.hcp.yervoy.com/pages/remms.aspx>
- Opdivo® (Nivolumab) Package Insert: [http://packageinserts.bms.com/pi/pi\\_opdivo.pdf](http://packageinserts.bms.com/pi/pi_opdivo.pdf)
- Management Algorithms for Adverse Events Associated with Immuno-oncology Agents (see Section 8.3.1).

Note: As durable disease stabilization and/or objective tumor response may be observed after early progression, it is recommended that, in the absence of toxicity requiring discontinuation in accordance with the package insert, all 4 doses of concurrent ipilimumab and nivolumab be administered over the initial 12 weeks, even in the setting of apparent clinical progression, provided the subject's performance status remains stable.

Even in the event of a dose delay, disease assessments should be performed according to standard of care on the originally scheduled study days.

Dose modifications for radiotherapy as a result of toxicity are allowed per the Investigator's assessment.

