### 3.1.9 Dose-limiting Toxicity

The DLT and MTD will not be defined or determined. A safety review will be conducted when 9 subjects have been accrued to Cohort A and completed the concurrent ipilimumab and nivolumab therapy. If  $\leq 7$  subjects have Grade 3 or 4 drug- or radiation-related AEs, the safety of Cohort A will be deemed acceptable and additional subjects will be accrued to Cohort B. The Cohort A assessment period for this evaluation will include the first 2 cycles of treatment, up to and including the pre-dose safety assessments scheduled for Cycle 3 (see Section 4.1.2).

Note: Grade 3 or 4 amylase or lipase abnormalities that are not associated with clinical symptoms will not be included in the Cohort A safety assessment described above.

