### **3.1.13 Interim Analysis**

An interim analysis of safety will be performed after 9 subjects in Cohort A have completed concurrent ipilimumab and nivolumab therapy in order to determine whether to proceed with enrollment into Cohort B (see Section 3.1).

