#### 4.1.2 Subject Evaluation & Statistics

The Intent-To-Treat (ITT) Population for safety and tolerability is defined as all subjects who receive at least one dose of study drug or RT. The Per-Protocol (PP) Population for safety and tolerability is defined as all subjects who received at least 75% of the scheduled doses of study drugs and RT over the first 2 cycles, as well as, respective safety assessments (up to and including the pre-dose assessments scheduled for Cycle 3) without major protocol violations over the entire Cohort A concurrent ipilimumab and nivolumab assessment period (as defined in Section 3.1.9).

For both cohorts, the overall analysis of safety and tolerability will be based on the ITT Population.

Appropriate summaries of AEs, laboratory data, and vital sign data will be presented. AEs will be listed individually per subject according to the NCI CTCAE, Version 4.03, and the number of subjects experiencing each AE will be summarized using descriptive statistics.

CONFIDENTIAL

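### The Cohort A safety count closes at Cycle 3 pre-dose whenever RT ended, so observation after the last fraction can run from 9 to 31 days among subjects treated as equally evaluable

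*Combined protocol and SAP*

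**What the plan says.** **When RT is given.** Section 8.5.6 says "Treatment will be initiated after the first dose of immunotherapy, but before the second dose of immunotherapy". The Synopsis, Sections 3.1 and 6.2, the note under Table 1 and flowchart footnote f give the same start-only rule. For the Cohort A course, Section 8.5.6 adds that subjects "should be scheduled to receive treatment on consecutive weekdays, no more than 5 days/week, over no more than 14 days". Table 1 sets "30 Gy delivered over 2 weeks in 10 fractions of 3 Gy each" against the Week 1 and Week 2 rows, with a dash at Weeks 4, 7 and 10. The flowchart marks RT in the Week 1 column only. On departures from schedule, Section 3.1.8 says "Dosing adjustment, delays, and discontinuations of RT should be managed in accordance with standard of care".

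**What the gate counts.** Sections 3.1 and 3.1.9 count subjects with Grade 3 or 4 events related to drug or radiation. Under Section 3.1.6 the toxicity "is considered to be acceptable in Cohort A if" no more than 7 of 9 subjects are affected. Section 3.1.9 limits the assessment period to the first two cycles, "up to and including the pre-dose safety assessments scheduled for Cycle 3".

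**Who is evaluable.** Under Section 3.1.11, a subject with a related Grade 3 or 4 event is evaluable, and item 1 puts no time limit on that event. A subject without one must meet the Per-Protocol definition in Section 4.1.2, which requires having "received at least 75% of the scheduled doses of study drugs and RT over the first 2 cycles", with the matching safety assessments.

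**When the review is held.** Section 3.1.13: "An interim analysis of safety will be performed after 9 subjects in Cohort A have completed concurrent ipilimumab and nivolumab therapy".

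**The concern.** The gate exists to judge the antibodies and RT together before Cohort B opens at 9 Gy per fraction. Its counting window is anchored to antibody cycles, and no minimum period of observation after RT is stated. If RT starts late in the permitted interval, much of the course falls after dose 2 and the period in which a radiation-related event can be counted is shorter. A late-RT subject with no event by Cycle 3 pre-dose still counts as a full event-free subject.

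An event just after the window closes is left out of the count, so truncation can only lower it. Section 3.1.6 says no historical controls exist for the triple regimen, so these nine subjects are the main evidence for the decision.

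**Working it through.** **Inputs**
- RT start: after dose 1 (Day 1) and before dose 2 (Day 22 ± 3), from Section 8.5.6 and the flowchart. Nominal start: Day 1 to Day 21.
- Course: 10 fractions on consecutive weekdays within 14 days (Section 8.5.6).
- Window close: Cycle 3 pre-dose, Day 43 ± 3 (Section 3.1.9 and flowchart).
- Fourth concurrent dose: Day 64 ± 3 (flowchart).

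**1. The plan's own figures.** Study day = 7 × (week − 1) + 1 gives Week 4 = Day 22, Week 7 = Day 43 and Week 10 = Day 64, as in the flowchart. The gate percentage is 7/9 = 77.8%, stated as 78%.

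**2. Course length.** Ten consecutive weekdays span 12 calendar days from a Monday start and 14 from any other weekday. Last fraction = start + 11 or start + 13.

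**3. Observation after the last fraction, nominal days** (43 − last fraction)
- Start Day 1: last fraction Day 12 or 14, so 31 or 29 days.
- Start Day 21: last fraction Day 32 or 34, so 11 or 9 days.

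The end points move slightly with convention. If RT cannot start on Day 1, the longest is 28 days (last fraction Day 15). If RT starts on Day 22 just before dose 2, the shortest is 8 days (last fraction Day 35).

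**4. Observation from RT start, nominal days**
- Start Day 1: 43 − 1 = 42 days.
- Start Day 21: 43 − 21 = 22 days.

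**5. Other readings of the schedule**
- Course complete within Weeks 1 and 2 (Table 1): last fraction Day 12 to 14, so 29 to 31 days.
- Start within Week 1 (flowchart mark): latest start Day 7, last fraction Day 20, so 23 to 31 days.

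**6. Visit windows**
- Shortest: dose 2 on Day 25, RT start Day 24, last fraction 24 + 13 = Day 37, Cycle 3 on Day 40, so 3 days. This puts doses 2 and 3 only 40 − 25 = 15 days apart.
- With doses 2 and 3 kept 21 days apart, the shortest is 9 days wherever dose 2 falls in its window.
- Longest: last fraction Day 12, Cycle 3 on Day 46, so 34 days.

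**7. Does the 75% rule exclude the late subject?** A Day 21 start delivers all ten fractions by Day 34, inside the first two cycles. The subject meets the RT part of the Per-Protocol definition. The rule measures RT delivered, not time observed afterwards.

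**8. How close the gate is to failing.** It fails at 8 or 9 of 9. At the 53% rate that Section 3.1.6 cites for the two antibodies, P(X ≥ 8) = 9 × 0.53⁸ × 0.47 + 0.53⁹ ≈ 0.03. The lost events change the decision only if the in-window count is 7 or fewer and the uncounted subjects would bring it to at least 8.

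**The case against.** The case against is substantial, and parts of it stand.

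- **RT is not unbounded.** A reader might infer that it has no completion limit at all. The documents do not support that: Section 8.5.6 schedules the course over at most 14 days, and the 9-day figure relies on that cap. Section 4.1.2 adds an indirect bound through the 75% rule. What is missing is a study day for completion, and RT delays are left to standard of care.
- **The schema may settle it.** On Table 1's Weeks 1 and 2 placement the spread almost vanishes. This stands as a limit on the point. But the table's own note repeats the start-only rule, so the table does not resolve the question.
- **Three days is not a fair minimum.** A reader might take it from the visit windows. It needs a 15-day gap between doses 2 and 3 under a three-weekly regimen; at 21 days apart the minimum is 9.
- **The late subject is not barely observed.** Radiation can contribute to toxicity from the first fraction, and even a Day 21 start leaves 22 days from RT start. On that measure the range is 42/22, about 1.9-fold.
- **Other oversight exists.** The review waits for completion of concurrent therapy, safety is reviewed on an ongoing basis (Section 4.1), the stopping rules in Section 3.1.14 are not tied to Cycle 3, and adverse events are collected to 100 days after the last drug dose (Section 7.1.5). This limits the harm, but it does not change which events enter the formal count.
- **No effect on the gate is shown.** Correct. The documents give no time course for radiation toxicity and no expected share of late starts, the study is descriptive, and the gate is deliberately lenient.

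**Conclusion.** The point holds in a limited form. The start-only rule and a window fixed to Cycle 3 pre-dose allow unequal observation after RT: 9 to 31 days after the last fraction, or 22 to 42 days from RT start, with all these subjects equally evaluable if event-free. This assumes nominal visit days, doses 21 days apart, ten consecutive weekday fractions without interruption, and that the start-only text governs. If Table 1's Weeks 1 and 2 placement governs, the range is 29 to 31 days and little remains beyond the inconsistency between passages.

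The direction is certain: a shorter window can only lower the count. The size is not known. A reader might infer that late RT would turn a failing Cohort A into a passing one; the documents give no basis for estimating that. The change is still worth making, because it affects which events enter the decision to open Cohort B and uses data already being collected.

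**What to change.** - In Section 3.1.9 and the Per-Protocol definition in Section 4.1.2, close the Cohort A counting window at the later of Cycle 3 pre-dose and a stated minimum period after the last RT fraction. Twenty-eight days is used here as an example; it is an assumption, not a figure from the documents, and the sponsor should confirm or replace it with a reason.
- Align Section 3.1.11 item 1 with that window, so that the qualifying event and the count share the same time limit.
- At the gate, report for each subject the days observed from RT start and from the last fraction.
- Reconcile Table 1 and the flowchart with the start-only text. The RT timing itself is the sponsor's clinical decision.

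**Cost.** Wording, and no new data. At nominal days there is no delay: the latest RT end plus the example period is 34 + 28 = Day 62, before the fourth dose on Day 64. At the visit-window extremes it is 37 + 28 = Day 65, against a fourth dose on Days 61 to 67, so the review could wait up to 65 − 61 = 4 days. RT delays could add to that.

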## 8.6 Exploratory Assessment of Correlative Immunologic Research

Peripheral blood and optional tumor samples (when available) will be collected as outlined in Section 3.2 and banked for testing at the end of the study. Separate instructions will be provided regarding the processing, storage and testing of these samples. Testing may include but may not be limited to the following:

- lymphocyte phenotype using markers such as ICOS, PD-1, and CD25
- the quantities of myeloid derived suppressor cells (MDSCs), defined as CD14+HLA-DRlow cells
- antibody and functional T cell responses to tumor associated antigens (i.e. NY-ESO-1) for relevant subjects
- serum cytokine levels such as TNF-alpha, IFN-gamma, IL-1beta, IL-2, IL-4, IL-5, IL-6, IL-8, IL-10, IL-12, and TGF-beta
- Serum and plasma microparticle and exosome nanoFACS and proteomic profiles
- T cell repertoire diversity in peripheral blood and tumor.

Additional investigational methods will be used to characterize and measure components of the immune response based upon the latest available technology.

---

CONFIDENTIAL

## 8.7 Abbreviations

AE	adverse event
ALT	alanine aminotransferase
AST	aspartate aminotransferase
CRF	Case report form
CTCAE	Common Terminology Criteria for Adverse Events
CTLA-4	Cytotoxic T lymphocyte-associated antigen 4
DCR	Disease control rate
DLT	dose-limiting toxicity
ECOG	Eastern Cooperative Oncology Group
eCRF	Electronic Case Report Form
FDA	Food and Drug Administration
GCP	Good Clinical Practice
GMP	Good manufacturing practice
HLA	Human Leukocyte Antigen
HNSCC	Head and neck squamous cell carcinoma
IB	Investigator Brochure
ICF	Informed Consent Form
ICH	International Conference on Harmonization
IL	interleukin
IND	Investigational new drug
irAE	Immune-related adverse event
irRC	immune-related response criteria
irRECIST	Immune-related Response Evaluation Criteria In Solid Tumors
IV	intravenous
IRB	Institutional Review Board
LICR	Ludwig Institute for Cancer Research
mAb	Monoclonal antibody
MDSC	myeloid derived suppressor cells
MTD	maximum tolerated dose
NCI CTCAE	National Cancer Institute Common Terminology Criteria for Adverse Events
NK	Natural killer
OAR	Organ at risk
ORR	Objective Response Rate
OS	Overall survival
PBMC	Peripheral blood mononuclear cell
PD-1	Programmed death-1
PD-L1	Programmed death ligand 1
PFS	Progression free survival

---

CONFIDENTIAL

PK	Pharmacokinetics
Q2W	Every 2 weeks
Q4W	Every 4 weeks
Q6W	Every 6 weeks
Q12W	Every 12 weeks
RECIST	Response Evaluation Criteria in Solid Tumors
RT	Radiotherapy
SAE	Serious Adverse Event
SD	Standard Deviation
TME	Tumor microenvironment
TIL	tumor-infiltrating lymphocyte
ULN	Upper limit of normal

